**Table 1 - SVR12 rates in clinical trials:**

Population and treatment duration	Genotype	SVR12 Paritaprevir/r + Ombitasvir + Dasabuvir + RBV	SVR12 Paritaprevir/r + Ombitasvir + Dasabuvir
Non-cirrhotic, treatment-naïve (12 weeks)	1a	95-97% (SAPPHIRE-I, PEARL-IV)	90% (PEARL-IV)
	1b	98 – 99.5% (SAPPHIRE-I, PEARL-III)	99% (PEARL-III)
Non-cirrhotic, treatment- experienced (12 weeks)	1a	96% (SAPPHIRE-II)	n.a.
	1b	97% (SAPPHIRE-II, PEARL-II)	100% (PEARL-II)

These results suggest that the ABBVIE REGIMEN with RBV is the optimal regimen for genotype 1a infected patients, while patients with genotype 1b do not require RBV.

The TURQUOISE-II [60] study explored the efficacy of the ABBVIE REGIMEN in the traditionally most difficult-to-treat cirrhotic patients. This large study enrolled exclusively genotype 1 infected patients with cirrhosis, including treatment-naïve and treatment-experienced individuals. All patients received the ABBVIE REGIMEN with RBV and were

**Confidential Information**

randomized to 12 or 24 weeks of therapy. Overall 92% and 96% of patients achieved SVR following treatment for 12 or 24 weeks, respectively. Analysis of subgroups demonstrated that the small difference in SVR between treatment arms was due largely to the subgroup of genotype 1a treatment-experienced prior null responders treated for 12 weeks who achieved an SVR of 80%. This subgroup of patients achieved an SVR of 93% when treated for 24 weeks. Among genotype 1a infected patients, partial responders and relapsers had higher SVR rates than null responders in the 12 week treatment group, while similar SVR rates were seen among the null responders, partial responders and relapsers treated for 24 weeks, suggesting that the longer duration of 24 weeks is required only for cirrhotic genotype 1a null responders. SVR rates were very high across all subgroups in genotype 1b treatment-experienced patients treated for 12 and 24 weeks.

The ABBVIE REGIMEN has been studied with and without RBV in over 2,300 patients in Phase III trials across a variety of patient populations including those with compensated cirrhosis. Based on Phase III data, the ABBVIE REGIMEN, with or without RBV, was well tolerated with a low discontinuation rate. Adverse events (AEs) were typically mild, and many of the AEs and laboratory abnormalities reported were attributable to the presence of RBV. However, these AEs were much milder than observed when RBV was given in combination with interferon. Transient, asymptomatic serum alanine aminotransferase (ALT) elevations were observed at a low rate, were not associated with hepatic dysfunction and generally resolved with ongoing treatment. A disproportionate number of the cases were in women on concurrent systemic ethinyl-estradiol-containing therapy (i.e., contraceptives) and discontinuation of the hormonal therapy with continuation or brief interruption of the ABBVIE REGIMEN led to resolution in serum ALT elevation. Transient elevations in serum bilirubin (predominantly indirect) were observed in subjects receiving the ABBVIE REGIMEN with RBV, related to the inhibition of the bilirubin transporters, organic anion-transporting polypeptides (OATPs) 1B1/1B3, by ABT-450 and RBV-induced hemolysis. Bilirubin elevations occurred after initiation of treatment, peaked by study Week 1, and generally resolved with ongoing therapy. Bilirubin elevations were not associated with aminotransferase elevations. The frequency of indirect bilirubin elevations was lower among subjects who did not receive RBV.

Response of CHC genotype 4 was assessed in the phase II study PEARL-I in which 86 treatment-naïve patients were randomized to the 2 DAA combination of Paritaprevir/r – ombitasvir with vs. without RBV for 12 weeks. The SVR was 100% with RBV vs. 91% without RBV [61]. No serious SAEs or AEs leading to discontinuation were reported.

These results from pivotal studies are encouraging and the new interferon-free regimens might provide physicians with the armamentarium to cure the vast majority of patients

---

Confidential Information

infected with CHC. However, the medical community is expecting data which show how these results translate into routine clinical practice particularly after the experience with the first protease inhibitors which were available to physicians and where the outcome in everyday life and especially the tolerability was far less favorable in certain difficult-to-treat patient subgroups than expected from the development trials [62] [63].

## 7.2 Rationale

The ABBVIE REGIMEN ± RBV for the treatment of CHC has been shown to be safe and effective in randomized controlled clinical trials with strict inclusion and exclusion criteria under well controlled conditions.

The ABBVIE REGIMEN has become available in Germany for the treatment of CHC in January 2015.

The rationale for this observational study is to determine how the efficacy and safety of the ABBVIE REGIMEN as demonstrated in pivotal trials translates into real world everyday clinical settings, evaluating its effectiveness. Whereas efficacy can be defined as a measure of the capacity of a treatment to produce the desired effect in a controlled environment, such as in a randomized controlled trial, effectiveness is 'the extent to which a drug achieves its intended effect in the usual clinical setting' [64]. Effectiveness trials typically have limited exclusion criteria and will involve the broader patient populations in routine clinical practice, treated per local label, which might include patients with heterogenous compliance patterns and patients with significant comorbid conditions and could be used to model and disseminate best practices. Effectiveness research allows for external patient-, provider-, and system-level factors and can therefore be relevant for health-care decisions by both providers in practice and policy-makers [65].

This observational study is the first effectiveness research examining the ABBVIE REGIMEN ± RBV, used according to local label, under real world conditions in Germany in clinical practice patient populations.

During the last decade when dual therapy with pegIFN plus RBV was standard of care for the treatment of CHC, management of patients and clinical outcome were improved following the discovery of predictive factors of virological response, often in observational studies with large data bases [66]. Thus treatment could be targeted to patients most likely to respond and futile treatment stopped in patients with a low likelihood of virological cure. HCV genotype and subtype, baseline viral load, fibrosis stage, age, treatment exposure and on-treatment virological response proved to be useful predictors

---

### Confidential Information

for the eradication of HCV in everyday clinical practice [27]. More recently the discovery of a genetic disposition of the Interleukin 28B (IL28B) single nucleotide polymorphism (SNP) contributed further to our understanding of virological responses to treatment [67]. For new interferon-free treatment regimens knowledge of predictive factors of virological response is extremely sparse and several of the now well established predictors of response were not initially identified through analyses of the development trials. This observational study may play an important part in bridging the data gaps and could help identify predictive factors of virological response in everyday clinical settings which were not detected in interventional trials and which could be used to further optimize treatment with the interferon-free ABBVIE REGIMEN in the future.

The label of the ABBVIE REGIMEN will vary according to HCV genotype/subtype and stage of liver disease. It is therefore relevant to understand the pattern of use and outcome in daily clinical practice. In addition, this study will provide data on the impact of adherence on treatment outcomes in everyday settings which may help treating physicians to improve the management of patients under their care.

The aim of this observational study is to provide evidence of the effectiveness and patient reported outcome (PRO) or work productivity of the ABBVIE REGIMEN ± RBV in a real world setting across clinical practice patient populations.

## **8.0 Research Question and Objectives**

### **8.1 Research Question**

What is the effectiveness and patient reported outcome or work ability of the interferon-free ABBVIE REGIMEN ± RBV in patients with CHC in a real life setting across clinical practice patient populations?

### **8.2 Objectives**

#### **8.2.1 Primary Objective**

1. To describe in routine clinical practice the effectiveness of the interferon-free ABBVIE REGIMEN ± RBV in patients with CHC as evidenced by SVR12.

#### **8.2.2 Secondary Objectives**

1. To provide real world evidence for predictive factors of virological response
2. To document the effect of the ABBVIE REGIMEN ± RBV on PROs and work productivity in the German population

---

Confidential Information

3. To describe the pattern of real world use of the ABBVIE REGIMEN ± RBV with respect to different patient and treatment characteristics
4. To evaluate the influence of adherence on treatment outcome in routine clinical practice
5. To describe the tolerability of the ABBVIE REGIMEN ± RBV
6. To collect information on co-morbidities and concomitant medication in the German population

## 9.0 Research Methods

### 9.1 Study Design

This is a prospective, multi-center observational study in patients receiving the interferon-free ABBVIE REGIMEN with or without RBV. The prescription of a treatment regimen is at the discretion of the physician in accordance with local clinical practice and label, is made independently from this observational study and precedes the decision to offer the patient the opportunity to participate in this study.

Adult patients chronically infected with HCV, receiving the interferon-free ABBVIE REGIMEN will be offered the opportunity to participate in this study during a routine clinical visit at the participating sites.

After written patient authorization has been obtained, patient data including demographic data, HCV disease characteristics, co-morbidities, co-medication, treatment details, and laboratory assessments as recorded in the patient's medical records (source documentation) will be documented in the electronic case report form (eCRF) Patients will be observed for the duration of the ABBVIE REGIMEN therapy and for up to 48 weeks after treatment completion. No patient identifiable information will be captured, a unique patient number will be automatically allocated by the web based eCRF system once the investigator or designee creates a new patient file.

This study is focusing on collecting real-world data. Follow-up visits, treatment, procedures and diagnostic methods will follow physicians' routine clinical practice. The observational study period entails the following data collection schemes, data documented will be those closest to the time windows as indicated in Figure 1:

[figure not shown]
- 12-week treatment regimen: five visits plus two interim data collection windows
- 24-week treatment regimen: five visits plus three interim data collection windows

This schedule is based on the anticipated regular follow-up for patients undergoing treatment for CHC.

---

Confidential Information

Figure 1 - Study Flowchart

## 9.2 Setting

For overall research design and observational documentation schedule refer to Section 9.1 and 9.4.1 as well as to Figure 1.

### 9.2.1 Target Population

Patients are eligible for observation in this cohort if the following applies:

- Treatment-naïve or -experienced adult male or female patients with confirmed CHC, genotype 1 or 4, receiving combination therapy with the interferon-free ABBVIE REGIMEN ± RBV according to standard of care and in line with local label.
- If RBV is co-administered with the ABBVIE REGIMEN, it has been prescribed in line with the current local label (with special attention to contraception requirements and contraindication during pregnancy)
- Patients must voluntarily sign and date a patient authorization to use and/or disclose his/her pseudonymized health data prior to inclusion into the study
- Patient must not be participating or intending to participate in a concurrent interventional therapeutic trial

#### Confidential Information

### **9.2.2 Study Duration**

This is a prospective, observational study. The inclusion period will be approximately 12 months and the observational period of the study will be from baseline visit until 48 weeks post-treatment.

The observational period for patients receiving 12 weeks of ABBVIE REGIMEN will be max. 60 weeks (12 weeks treatment and 48 weeks post-treatment observation) and for patients receiving 24 weeks of ABBVIE REGIMEN the observational period will be max. 72 weeks (24 weeks treatment and 48 weeks post-treatment observation).

### **9.2.3 Termination Criteria**

For patients who terminate the ABBVIE REGIMEN prematurely for whatever reason the EoT eCRF page should be filled in and the reason for treatment discontinuation should be documented. If the reason for ABBVIE REGIMEN discontinuation is due to an SAE, the event must be reported to AbbVie within 24 hours of physician awareness (see Section 11.5).

If, in such patients, there is evidence of virological response during therapy or at EoT, the SVR12, SVR24 and SVR48 pages should be completed if respective data is available.

### **9.2.4 Investigator Selection Criteria**

University centers and outpatient clinics qualified by training and experience in the management of patients with CHC will be selected to participate in this study. The AbbVie Affiliate Medical Director will ensure that sites participating in the study are representative of the medical practice in the country, have the ability to conduct the study and their availability of the target patient population. The type of the participating treating institute will be documented in the eCRF.

## 9.3 Variables

### 9.3.1 Primary Variable

- The percentage of patients achieving SVR12 (HCV RNA <50 IU/mL 12 weeks [i.e. ≥70 days] after the last actual dose of the ABBVIE REGIMEN)

### 9.3.2 Secondary Variables

- 
- Type of treatment regimen (± Dasabuvir, ± RBV, intended and actual combination, dose and duration)
- Patient adherence
- Serious and non-serious adverse events and pregnancy occurrences
- Questionnaire scores on PROs: Chronic Illness Therapy-Fatigue (FACIT-F), Work Productivity and Activity Impairment (WPAI), Burden of Suffering (PRISM), Patient Activation Measure (PAM-13)
- Co-morbidities and concomitant medication
- HCV relapse or reinfection after achieving SVR12 until post treatment week 48

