**Confidential Information**

- **Laboratory data**

- Key clinical chemistry

- ALT
    - AST
  
    - $\gamma$ -GT
    - Total bilirubin
    - Albumin
    - Creatinine
  - Remarks  
including ULN  
including ULN,  
APRI and FIB-4, will be calculated  
  
  
  
  
  
  
  
  
  
creatinine clearance will be calculated

- Key hematology

- Hb
    - Platelets
    - Prothrombin time
  - or INR

- Virology

- HCV RNA
  - quantitative/ qualitative HCV RNA PCR test, see 9.4.1.4

- HIV-infected patients only

- CD 4 count
    - HIV RNA
  - most recent assessment  
in copies/mL

- **Tolerability (sAEs, see 11.4) and pregnancies (see 11.6)**
- **Patient questionnaires see table 2 and 9.4.1.6**

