**Table 2 - Data Documentation Schedule**

Assessment/ Procedure (only available data to be collected; no diagnostic or monitoring procedures to be applied to the patients apart from those of routine clinical practice)	Baseline	Treatment Period			Post-treatment (PT) Period			
		On-treatment visits	Mid treatment visit for pts receiving 24 weeks of therapy	EoT b	Early PT visit	SVR 12 visit	SVR 24 visit	SVR 48 visit
Patient authorization	X a							
Demographic information	X							
IL28B	X							
Relevant CHC disease characteristics	X							
Liver fibrosis stage	X					X		X
CHC treatment history	X							
HCV genotype and subtype	X							
HCV RNA samples	X	X	X	X	X	X	X	X
Clinical chemistry and hematology	X	X	X	X	X	X	X	X
ABBVIE REGIMEN initiation documentation	X							
ABBVIE REGIMEN adherence		X	X	X				
Concomitant medication	X	X	X	X				
Relevant medical history, co-morbidities	X							
sAE, AE and pregnancy reporting	X	X	X	X	X c	X d	X d	X d
For patients receiving RBV: Evidence, in accordance with local label, that female patient or female partner of male patient is not pregnant	X							
Patient questionnaires: FACIT-F	X	X	X	X		X		X
Patient questionnaire: WPAI	X			X		X	X	
Patient questionnaire: PRISM	X					X		X
Patient questionnaires: PAM-13	X			X				
Patient questionnaire: PSP e (U f )			X		X			
Patient questionnaire: PSP e (U f & S g )		X		X		X		

Abbreviations: EoT = End of Treatment (at Week 12 or 24 or at premature discontinuation),  
PT = Post-Treatment

- a Written patient authorization must be obtained before any data documentation in the eCRF
- b Patients who prematurely discontinue should return to the site to document EoT data
- c Tolerability documentation until PT week 4
- d Pregnancy reporting for patients treated with DAA plus RBV
- e applicable for patients enrolled in the PSP
- f Utilization
- g Satisfaction

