#### 4.1.2 Secondary Parameters

The secondary effectiveness endpoints are:

- The percentage of patients with virological response (HCV RNA  $< 50$  IU/mL) at EoT (defined as last intake of ABBVIE REGIMEN or ribavirin)
- The percentage of patients with relapse (defined as HCV RNA  $< 50$  IU/mL at EoT followed by HCV RNA  $\geq 50$  IU/mL)
- The percentage of patients with breakthrough (defined as at least one documented HCV RNA  $< 50$  IU/mL followed by HCV RNA  $\geq 50$  IU/mL during treatment).
- Rapid virological response at week 4 (RVR 4, i.e. patients with HCV RNA  $< 50$  IU/mL at week 4)
- Sustained virological response 24 weeks after EoT (SVR24, i.e. patients with HCV RNA  $< 50$  IU/mL 24 weeks after EoT)
- Sustained virological response 48 weeks after EoT (SVR48, i.e. patients with HCV RNA  $< 50$  IU/mL 48 weeks after EoT)
- The number and percentage of patients meeting each and any of the following SVR12 non-response categories:
  - On-treatment virologic failure (breakthrough [defined as above] or failure to suppress [each measured on-treatment HCV RNA value  $\geq 50$  IU/mL])
  - Relapse (defined as HCV RNA  $< 50$  IU/mL at EoT followed by HCV RNA  $\geq 50$  IU/mL post-treatment for subjects who complete treatment [not more than 7 days shortened])
  - Premature study drug discontinuation with no on-treatment virologic failure

- Missing SVR12 data and/or none of the above criteria

Further secondary variables are:

- Type of treatment regimen ( $\pm$  Dasabuvir,  $\pm$  RBV, intended and actual combination, dose and duration)
- Adherence
  - Percentage of the DAA dose taken in relation to the target dose of DAA (cumulative dose taken divided by target dose in percent)
  - Percentage of the RBV dose taken in relation to the target dose of RBV (cumulative dose taken divided by target dose in percent)
  - Percentage of missed RBV treatment days in relation to the target number of RBV treatment days
- Co-morbidities and concomitant medication
- Serious and non-serious adverse events and pregnancy occurrences
- Questionnaires on PROs: e.g. PAM-13, FACIT-Fatigue, PRISM and work productivity and activity impairment (WPAI) questionnaire prior to treatment initiation, at EoT as well as 12, 24 and 48 weeks after EoT

No data will be imputed for any effectiveness or safety analyses except for the analyses of the HCV RNA endpoints and PRO questionnaires (if applicable). For further details see sections 4.2.3 and 4.2.7.2.3, respectively.

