**Table 3 - Analysis Time Windows for HCV RNA**

Phase	Time point	Time Window
Pre-Treatment	Baseline	Last value prior to start of study treatment (i.e. $\leq$ study day 1)
On-treatment		Study day during treatment period^# (Study day 1 = first treatment day)
Treatment Week	4 (RVR*)	15 - 42^
EoT	Actual EoT	Study day of last dose# (28 days prior to last dose - 7 days post last dose)
Post Treatment	12 weeks (SVR 12 window)	$\geq$ 70-126 days post last dose
	24 weeks (SVR24 window)	127-210 days post last dose
	48 weeks (SVR48 window)	> 210 days post last dose

^values must also be  $\leq$  7 days post last dose

#  $\geq$ study day 2

\*RVR = rapid virological response

All reported safety laboratory test results will be assigned to one of the time points using the time windows specified in the table below.

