#### **4.2.6.3 CHC treatment history**

For treatment-experienced patients the most recent prior treatment and the outcome to prior treatment as reported by the investigator in the eCRF (Null response, Partial response, Breakthrough, Relapse, Sustained virological response (SVR) followed by reinfection, Discontinued [and none of the above], Unknown / None of the above) will be summarized in frequency tables. In addition to the frequency of each medication (IFN alpha, PEG IFN-alpha, IFN NOS, PEG IFN NOS, Ribavirin, DAA), the frequency of the combinations (pegIFN alpha + RBV, IFN alpha + RBV, XXX) will be summarized.

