##### 4.2.7.2 Secondary Variables

###### 4.2.7.2.1 Secondary Effectiveness Variables

###### Response

For the other response rates (i.e. RVR, SVR24 , SVR48, EoT response rate, relapse rate, viral breakthrough), the simple percentage of patients and a two-sided 95% confidence interval (CI) of the percentage will be computed (based on the Wilson's score method) as well. The RVR and EoT response rates will be reported for CP and the SVR24 and SVR48 rates will be reported for the respective CPSFU, stratified by genotype and cirrhosis status and overall. The relapse rates will be estimated stratified by SVR window (i.e. during SVR12 window=relapse12, during SVR24

window=relapse24, after SVR24 window=relapselate) and stratified by genotype and cirrhosis status and overall in patients of the CP with EoT response who fulfilled the following criteria:

- completed treatment as defined previously,
- had at least one HCV RNA measurement  $\geq 70$  days post-treatment or was a treatment failure between EoT and 70 days post-treatment.

Viral breakthrough rates [defined as at least one documented HCV RNA  $<50$  IU/mL followed by HCV RNA  $\geq 50$  IU/mL during treatment] will be estimated overall and stratified by genotype and cirrhosis status in all patients of the CP, who have at least one undetectable or unquantifiable, on-treatment HCV RNA measurement and at least one on-treatment or EoT measurement thereafter.

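### The SAP does not carry over the protocol's secondary variable of relapse or reinfection after SVR12, so reinfections in treatment completers would be reported as late relapse

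*Protocol*

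**What the plan says.** **Protocol.** Section 9.3.2, and the abstract's list of secondary variables, include "HCV relapse or reinfection after achieving SVR12 until post treatment week 48". Section 9.7.3.2 separately defines a relapse endpoint: HCV RNA below 50 IU/mL at EoT, then 50 IU/mL or more. It does not say how reinfection is to be recognised. In Table 2 the row "HCV genotype and subtype" is marked at baseline only. Post-treatment virology in 9.4.1.3 is HCV RNA alone ("quantitative/ qualitative HCV RNA PCR test, see 9.4.1.4").

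**SAP.** Section 4.1.2 lists "The percentage of patients with relapse (defined as HCV RNA" below 50 IU/mL at EoT and 50 IU/mL or more afterwards. The joint variable from Protocol 9.3.2 is absent. Under Response in 4.2.7.2.1, "The relapse rates will be estimated stratified by SVR window": relapse12, relapse24 and a late category after the SVR24 window. The denominator is core-population patients with EoT response who "completed treatment as defined previously" and who have an HCV RNA value at least 70 days post-treatment or failed earlier. In Table 3 the row "48 weeks (SVR48 window") starts after day 210 and has no upper limit.

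The SAP mentions reinfection once, in 4.2.6.3, as an outcome of earlier therapy: "Sustained virological response (SVR) followed by reinfection". Neither the SVR12 non-response categories in 4.2.7.2.1 nor the study-termination reasons in 4.2.5 include it.

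**The concern.** After a documented SVR12, relapse and reinfection have opposite meanings. Relapse is failure of the regimen to hold; reinfection is a new exposure in a patient who was cured. The protocol acknowledges both by naming them together. The SAP keeps one name and applies it to whatever recurs in its denominator, so late relapse would overstate loss of effect, and SVR24 and SVR48 would understate durability, by however many reinfections occur.

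The error need not be even across patients. SAP 4.2.6.4 records active injection drug use and opiate substitution, and 4.2.4 lists drug-user units among the site types. Relapse tables were repeated by opiate substitution in the third and fourth interim analyses, and the fifth is structured by it. If re-exposure is commoner in that group, a difference in relapse could appear there with no difference in drug effect.

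**Working it through.** The documents state no relapse or reinfection figure, so there is none to reproduce. The main check is a comparison of definitions.

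**1. The variable against its replacement**

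| Element | Protocol 9.3.2 | SAP 4.1.2 and 4.2.7.2.1 |
|---|---|---|
| Event | Relapse or reinfection | Relapse only |
| Starting condition | SVR12 achieved | EoT response and completed treatment |
| End of period | Post-treatment week 48 | No upper limit after day 210 |

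The reinfection half of the event and the SVR12 condition are both lost. The SAP explains other departures from the protocol (the 126-day bound in 4.1.1, the replaced shift tables in 4.2.8.4) but not this one.

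**2. Where a reinfected patient lands.** Take a core-population patient who completes treatment, responds at EoT, has HCV RNA below 50 IU/mL at day 84, and is then reinfected.

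- *Viraemic at day 170:* relapse24, and SVR24 failure. SVR12 stands.
- *Viraemic at day 336 only:* late relapse, and SVR48 failure. If the day 127–210 window is empty, flanking cannot fill it because the later value is positive. That value is then imputed backward (SAP 4.2.3), so SVR24 also fails.
- *Same patient without the day 84 value, first later value positive:* backward imputation makes the patient an SVR12 failure as well.

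No route leads to a reinfection category.

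**3. Scale, on assumptions.** From the documents: 620 evaluable patients and 95% SVR12 (SAP 3.2), so 0.95 × 620 = 589 responders. Day 84 to day 336 is 252 / 365.25 = 0.69 years. *Assumed, not in the documents:* opiate-substitution share 10–30%; reinfection 2–5 per 100 person-years in that group and none elsewhere; true relapse after SVR12 0.2–0.5%; everyone followed and tested.

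- Reinfections = 589 × share × rate × 0.69. Low: 589 × 0.10 × 0.02 × 0.69 = 0.8. High: 589 × 0.30 × 0.05 × 0.69 = 6.1.
- As a share of responders: 0.8 / 589 = 0.1% to 6.1 / 589 = 1.0%.
- True late relapses: 589 × 0.002 = 1.2 to 589 × 0.005 = 2.9.
- Within the opiate-substitution group the added risk is 0.02 × 0.69 = 1.4% to 0.05 × 0.69 = 3.4%.

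Both counts are single digits, and under these assumptions either cause could be the larger. Testing is at the physician's discretion, so fewer events of both kinds would be seen.

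**The case against.** **The protocol defines relapse the same way.** This stands. Section 9.7.3.2 uses essentially the SAP's rule, and the 9.3.2 variable is a composite that never asks for the two causes to be separated. The SAP also already shows later windows apart from the first. The defect is therefore an omitted protocol variable and a label that claims too much, not a conflict over what relapse means.

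**Every return of viraemia is called relapse.** A reader might infer this, but the text does not support it. The rate is limited to core-population completers with EoT response. In the SVR12 non-response table, other post-treatment viraemia can fall under premature discontinuation or insufficient virological response.

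**The primary result is compromised.** This is not supported either. Reinfection after day 126 leaves a measured SVR12 intact; the exceptions are early reinfection and the empty-window case.

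**Most late relapses would be reinfections.** Pairing opposite extremes of the assumptions above gives 0.8 / (0.8 + 2.9) = 22% to 6.1 / (6.1 + 1.2) = 84%. All three driving rates come from outside the documents, so no share should be quoted as a finding.

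**A changed genotype would settle the cause.** It would not do so safely. SAP 4.2.1 admits genotype 1 and/or 4 and pools mixed, other and unknown genotype 1 subtypes with G1a, so a later 1b or genotype 4 result need not be a new infection. Reinfection with the same genotype would be missed.

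**The eCRF may have a reinfection entry.** It may; the eCRF is not among the documents. No SAP analysis uses one.

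**Opiate substitution is not the main stratifier throughout.** This is correct. The fourth interim analysis is structured by genotype and cirrhosis and repeated by age and by opiate substitution; only the fifth is built on opiate substitution. The relapse table in SAP Table 8 is by genotype and cirrhosis.

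**Conclusion.** The point holds in limited form. A named protocol secondary variable is missing from the SAP without explanation, and the SAP's rule would report reinfections in core-population completers with EoT response as relapse24 or late relapse, and as SVR24 or SVR48 failures when viraemic in those windows. The effect is on descriptive secondary rates and on interim tables split by opiate substitution. The primary SVR12 estimate is largely unaffected.

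The size cannot be derived from the documents. The illustration suggests about 0.1 to 1 percentage point of responders, resting on assumed opiate-substitution share, reinfection rate and complete testing. The reason to act is that late relapses are also expected to be few, so a handful of misnamed events could alter how the rate reads. The correction should be made, but nothing in the primary analysis depends on it.

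**What to change.** In SAP 4.1.2 and 4.2.7.2.1:

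1. Restore the variable from Protocol 9.3.2.
2. Keep *relapse* for viraemia that returns before SVR12 is documented. State whether an SVR12 obtained by flanking imputation counts as documented.
3. Report the first HCV RNA of at least 50 IU/mL after documented SVR12 as *recurrent viraemia (relapse or reinfection)*, overall and by opiate substitution.
4. Footnote the SVR24 and SVR48 rates to say that failures after documented SVR12 may include reinfection.
5. Where a repeat genotype or subtype, or an investigator's report of reinfection, is already available, list the case descriptively as *suggestive of reinfection*; otherwise list it as *undetermined*. Do not classify automatically on a genotype change.

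The cost is SAP wording, a row in the relapse output and its shell, and a short listing. No extra test is needed, which suits the non-interventional design. The fix does not depend on a new eCRF field: with data collection ending around April 2018 and the fifth interim snapshot dated 18 December 2017, such a field would reach few visits.

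The downside is that most recurrences will stay unresolved between relapse and reinfection, and an early reinfection before documented SVR12 would still be called relapse.
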